Participants will complete an online screening questionnaire determining eligibility prior to the visit. Once deemed eligible, participants will come into the laboratory to give informed consent, and participate in health screening/physical exam and a vaping session in which they will learn to use the study device (Reflex, Evolv LLC, or similar) and sample 4 e-liquids at 3% nicotine concentration to determine whether they can vape both nicotine forms (free-base and protonated). The 4 e-liquids will vary based on flavor (unflavored and flavored) and protonation level (0-100%). The unflavored set of two e-liquids (0% and 100% protonation) are the preferred test articles, but if the participant cannot vape four puffs from each of them without coughing, then they will sample the flavored set of two eliquids (0% and 50% protonated) to determine if they can vape four puffs from each of them without coughing. Puffing topography captured by the study EC will be collected to determine the participant's typical puff volume for each e-liquid tested. If the participant cannot vape the test e-liquids without coughing, they will be deemed ineligible for further participation. Eligible participants will be given a study device and 1 pod of each test e-liquid to take home and practice using at least 3 days (20 puffs per day with the study device and until they feel comfortable using the device) so that they can become familiar with using the study device and the test e-liquids. After review of the topography data stored on the device, participants that vape small volumes (<20 mL per puff) may be deemed ineligible from further participation. Participants will also be provided instructions that they must remain nicotine abstinent for 12 hours before Visit #2 and Visit #3.

Visit #2:

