Following confirmation of 12-hour nicotine abstinence from combustible tobacco products via exhaled CO (<10ppm), and after confirmation that participants practiced at least 3 days with the device and pods using the test e-liquids, participants will be randomized to nicotine form (free-base or protonated) using either unflavored or flavored e-liquid (determined from Visit #1) and order of the focal area of scanning (head/neck or chest). Participants will also complete a questionnaire assessing several measures of evaluating the perceived abuse liability of the study e-liquids. Participants will complete a standardized 1-puff vaping bout using the same device, with the same e-liquid, flavor, and nicotine, propylene glycol, and glycerol concentration. Specifically, participants will be randomized to undergo a dynamic scanning sequence (either 0-15 min head and 5 min chest scan, or 0-15 min chest and 5 min head scan). The imaging agent, [¹¹C]-nicotine, will be delivered to the participant by the participant taking a single puff of the e-liquid (protonated or unprotonated), in prone position inside the PET scanner; puff duration and volume will be determined by the participant (ad libitum). After the first scanning session is complete, the participant will rest outside the scanner for a >1-hour washout period so that the [¹¹C]-nicotine can decay (6 half-lives). Participants will not be permitted to leave the PET center waiting lobby and cannot leave the facility (except for restroom breaks).

The participant will repeat the single puff vaping bout with the same e-liquid, but will be scanned according to the other dynamic sequence. At least a 1-week period should elapse between visits 2 and 3.

Visit #3:

Visit #3 is essentially identical to Visit #2, but the participant will conduct the two single puff vaping bouts using the e-liquid containing the other form of nicotine.

Visit	PET	CT - Anatomic
Visit #1: Informed consent; select test article; puffing topography	None	None
Visit #2a:	1 puff (ad lib) of [¹¹ C]-Nicotine with protonated nicotine 0-15 min head scan; 16-20 min chest scan	Head Chest
	WASHOUT PERIOD of >1 h	
Visit #2b:	1 puff (ad lib) of [¹¹ C]-Nicotine with protonated nicotine 0-15 min chest scan; 16-20	Chest Head
	min head scan	
	≥1 WEEK	
Visit #3a:	1 puff (ad lib) of [¹¹ C]-Nicotine with unprotonated nicotine 0-15 min head scan: 16-20	Head Chest
	min chest scan	
	WASHOUT PERIOD of >1 h	

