Visit #3b:	1 puff (ad lib) of [¹¹ C]-Nicotine with unprotonated nicotine	Chest Head
	min head scan	
	DEBRIEFING	

Table 1. Activities conducted during participant laboratory visits.

F. Recruitment Feasibility and Retention

i. Recruitment

A total of up to 30 current e-cigarette users (aged 21-50 years) will be recruited from the general community via targeted internet advertisements i.e., local newspaper, advertisements, craigslist, Facebook, Instagram, and Twitter as well as flyers and word-of-mouth advertising in the North Carolina Triad Area (Greensboro, Winston-Salem, and High Point). Based on our team's previous studies, we conservatively assume a 20% attrition rate. Participants will complete an online screener questionnaire, and those who meet the following eligibility criteria will be asked to take part in the study.

Inclusion criteria:

- A current e-cigarette user (≥1 vaping bout per day) for at least the past 6 months (confirmed by NicAlert saliva testing strip or similar test)
- 2) Between 21-50 years old
- 3) Willing to provide informed consent and abstain from all tobacco, nicotine, and marijuana use for at least 12 hours prior to visits 2 and 3
- 4) Willing to participate in 3 laboratory visits
- 5) Read, write, and speak English
- 6) If utilizing study provided rideshare services, will need to live within 20 miles from Wake Forest University

Exclusion criteria:

- 1) Self-reported diagnosis of lung disease including asthma, cystic fibrosis, or chronic obstructive pulmonary disease
- 2) Unstable or significant psychiatric conditions (past and stable conditions will be allowed)
- 3) History of cardiac event or distress within the past 3 months
- 4) Currently pregnant (as indicated by urine pregnancy test at the start of each laboratory visit), planning to become pregnant, or breastfeeding (women only)
- 5) Use of other tobacco products (e.g., cigarette, cigar, etc.) >5 days in the past month
- 6) Currently engaging in a tobacco product cessation attempt

Assessment of Eligibility

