EC Device: All participants will complete puffing sessions using an Evolv Reflex device (**Figure 2**), which is able to vape both FB and NSB e-liquid. Device specifications include: 750mAh battery, 3-25 watts output range, 2ml pod capacity, 37.5 grams weight, 1.0 amps of charging current, and 84mm x 300mm x 11mm dimensions with the pod installed. We will use the eScribe software available to retrieve information about the participant's use of the product in the field (and during the standardized puff session) including the number of puffs, puff duration, puff volume, flow rate, time of day puff was taken, wattage, coil temperature for each puff, and inter-puff-interval, which we view as a great strength. A new e-liquid pod will be used for each participant and each puffing session. Participants will be provided pre-filled and weighed e-liquid pods.

Figure 2. Study EC Device

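### The 12-hour abstinence rule covers all nicotine, but the only objective check at the scan visits is exhaled CO for combustible tobacco, in a sample of daily vapers

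*Combined protocol and SAP*

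**What the plan says.** **What is required.** The inclusion criteria in Section F.i ask participants to "abstain from all tobacco, nicotine, and marijuana use for at least 12 hours prior to visits 2 and 3". Section E.ii, Visit #1, has them told that "they must remain nicotine abstinent for 12 hours before Visit #2 and Visit #3".

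**What is checked.** Section E.ii, Visit #2, opens: "Following confirmation of 12-hour nicotine abstinence from combustible tobacco products via exhaled CO (<10ppm". For the next visit the text says "Visit #3 is essentially identical to Visit #2", so the same check applies. In Table 3, exhaled CO is the only biomarker row at Visits 2 and 3. The saliva test is marked at Visit 1 only, and its stated purpose in Section F.i is to establish user status ("confirmed by NicAlert saliva testing strip or similar test").

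**Who is enrolled.** Inclusion requires "A current e-cigarette user (≥1 vaping bout per day) for at least the past 6 months". Exclusion criterion 5 removes anyone with "Use of other tobacco products (e.g., cigarette, cigar, etc.) >5 days in the past month".

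**What else bears on abstinence.** Section H introduces the modified smoking-urges questionnaire expressly to corroborate the 12 hours and adds the Minnesota withdrawal scale. Table 3 marks both at Visits 2 and 3. Neither has a threshold or a consequence. Section I.i lists craving and withdrawal suppression among the outcomes to be compared.

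**What the device records.** Section F.iv says the eScribe software retrieves field use, including "time of day puff was taken". Section E.ii, Visit #1, uses the stored data to screen out small puff volumes. Nothing in the plan uses the time stamps to check the 12-hour window.

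**The concern.** The rule and its check do not cover the same products. The rule is about all nicotine. The check, by its own description, is about combustible tobacco, which these participants use seldom if at all. A participant who vaped on the morning of the scan, and smoked nothing, would pass the check as written.

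The scans and questionnaires are meant to compare two nicotine forms from the same abstinent state. Someone who has recently vaped plausibly has less craving and withdrawal left to relieve, so the pre-to-post changes described in Section I.i would be compressed. Puff duration and volume are ad libitum, so topography could be affected too. The crossover does not remove this, because a participant can be abstinent at one visit and not at the other.

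The two scales do not close the gap. Low craving at arrival may mean a lapse or simply a less dependent vaper. The plan does not say how to tell these apart or what to do in either case.

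**Working it through.** The plan states no lapse rate and no figure for the effect of a lapse, so there is nothing to reproduce. The check is a comparison of sections followed by an illustration.

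**Step 1: requirement against verification at Visits 2 and 3**

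| Product | Abstinence required? | Checked by CO, as described? | Other evidence |
|---|---|---|---|
| Combustible tobacco | Yes | Yes | Craving and withdrawal scales |
| Study e-cigarette | Yes | No | Scales; time-stamped log retrieved but not used for this |
| Participant's own e-cigarette | Yes | No | Scales |
| Other nicotine products | Yes | No | Scales |

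The products used daily are in the rows without an objective check.

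**Step 2: what the log could cover.** Section E.ii gives participants the device to practise with between Visits 1 and 2. Section F.iii pays for its return at Visit 2. No field use is described between Visits 2 and 3. The log can therefore show study-device puffs in the 12 hours before Visit 2. It cannot be relied on before Visit 3, and it says nothing about other devices.

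**Step 3: how many visits might be affected.** Inputs: up to 30 participants (Section I.i) and two scan visits each, so 30 × 2 = 60 visits. The per-visit lapse probability p is assumed, and lapses are taken as independent.

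- Expected lapsed visits = 60p. For p = 0.05, 60 × 0.05 = 3. For p = 0.20, 60 × 0.20 = 12.
- Probability of at least one = 1 − (1 − p)^60. For p = 0.05 this is 0.95; for p = 0.20 it exceeds 0.999.

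**Step 4: possible dilution.** Suppose lapses are equally likely under both forms, and that a lapse reduces the response by a fraction b. A form with true mean response μ then shows (1 − p)μ + p(1 − b)μ = (1 − pb)μ, and the contrast between forms shrinks by the same factor. With the variance held fixed, the sample size needed for the same power rises by 1/(1 − pb)². Take b = 0.5:

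| p (assumed) | 1 − pb | 1/(1 − pb)² |
|---|---|---|
| 0.05 | 0.975 | 1.05 |
| 0.10 | 0.95 | 1.11 |
| 0.20 | 0.90 | 1.23 |

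**Step 5: limits of the model.** If a lapse shifts the score by the same amount under either form, instead of scaling the response, the shift cancels on average and leaves only noise. Systematic bias between forms needs lapses that differ by form or period. Added noise is not in the table, because the variance was held fixed.

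**The case against.** The strongest reply is that the plan does address abstinence beyond CO. It names a craving scale for exactly this purpose, adds a withdrawal scale, and collects both at each scan visit. It also foresees post-minus-pre comparisons, which allow for baseline differences in part. This is a pilot, and its only stated sample-size basis is the dose released, not the subjective effects. These points stand. They limit the weight of the concern, but they do not supply an objective check on vaping or a rule for acting on the scales.

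Several stronger readings are tempting and are not supported:

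- **That lapsed visits cannot be identified at all.** The scales give some evidence. It is weak and has no rule attached, but it exists.
- **That staff already use the log to confirm the three practice days.** Section E.ii requires that confirmation without saying how it is made. The only stated pre-scan use of the log is the puff-volume screen.
- **That the loss is large.** If a lapsed visit showed no response at all and 20% of visits lapsed, the factor would be 0.80 and the sample-size equivalent 1/0.80² = 1.56. Total loss of response is the extreme case, and neither assumption has a source in the documents.
- **That the log would solve the problem.** It covers one device before one of the two visits.

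A further caution concerns liking and satisfaction. As extracted, Table 3 marks those questionnaires at Visit 2 only. If that is how the table reads, they have no scheduled within-person contrast to dilute, and the point then rests on craving, withdrawal and topography.

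**Conclusion.** The concern holds as a mismatch between rule and check. Abstinence from all nicotine is required before both scan visits, and the only objective verification is limited to combustible tobacco in people who vape every day. The craving and withdrawal scales are weak, unformalised evidence and double as outcomes.

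The consequence is added noise and possible dilution of the form contrast on the subjective outcomes, perhaps also on topography. Its size is unknown. The range of 0.975 to 0.90 (1.05 to 1.23 times the sample size) rests on assumed lapse rates of 5% to 20%, half-blunting that acts multiplicatively, equal lapse rates under both forms, and unchanged variance. It is an illustration, not an estimate.

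This is a worthwhile improvement at low cost, not a threat to the study's validity.

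**What to change.** 1. In Section E.ii, Visit #2, reconcile the abstinence wording with the Visit #1 instruction and the inclusion criterion. Keep CO and state that it addresses combustible products.
2. At Visits 2 and 3, record the date and time of last use of any nicotine product, with the product type.
3. At Visit 2, before randomization, check the eScribe time stamps for study-device puffs in the prior 12 hours and record the result.
4. State that the craving and withdrawal scales are completed before the puff, and adjust the subjective outcomes in Section I for those scores.
5. Add a sensitivity analysis excluding visits that fail the 12-hour rule on items 2 or 3. Failures at Visit 3 arise after randomization, so this should support the main analysis, not replace it.

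The cost is one question per visit, one log check and one extra analysis, with no new assay. The downside is that last use is self-reported, and the log covers only the study device and only the window before Visit 2. Lapses on a participant's own device would be detected only by self-report.

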All research staff will have completed Human Subjects and HIPAA training. Standard operating procedures (SOP) will be developed and all staff will be trained to ensure adherence to the SOP. As is standard practice for our team's current studies, each visit will have its own checklist of specific measures to be completed and the order in which they are to be administered. To reduce data entry errors, we will use secure computer-based questionnaires for participants to complete, including daily diaries. All key on-site personnel will meet face-to-face weekly throughout the entire study. Off-site investigators will also participate in these weekly meetings during the first year for project start-up; however, this will be reduced to every other week as the study progresses. During these meetings, recruitment, enrollment, data collection, data monitoring results, and any concerns or issues that may arise will be discussed. We will also plan for all key personnel to meet (virtually) at the Ohio State University and Wake Forest University sites in the first year for start-up and then in the final year to discuss analyses, manuscripts, and future research based off of this study.

H. Measures

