All measures, summarized in Table 3, have been used and validated previously by our team. Questionnaire data will be collected electronically into a secure, encrypted database (REDCap) by a trained research assistant. Sociodemographic measures will assess participant age, sex, marital status, ethnicity, employment status, occupation, years of education, and socioeconomic status. Tobacco use history will assess years of tobacco use, age of first use, tobacco type, brand, frequency, quantity, and duration of use all of nicotine/tobacco products including cigars, cigarillos, little cigars, pipe tobacco, chewing tobacco, snuff, snus, EC/vape/mod/APV/e-hookah, and hookah tobacco. EC Dependence will be measured with a modified 12-item Cigarette Dependence Scale²¹. Abuse liability of products will be measured by self-report of subjective effects, including an adapted version of the Drug Effects/Liking Questionnaire will assess the desire and liking of both study products, positive and negative effects (i.e., side effects), and perceived strength and effectiveness. The modified Cigarette Evaluation Questionnaire (mCEQ)²² will also assess subjective responses to e-cigarettes (e.g., reward, satisfaction)^{23,24}. EC puff topography will be measured with the study EC device, including measures of puff count, puff duration, inter-puff-interval, puff flow rate, average puff volume, and total puff volume. Puff topography is a validated and sensitive behavioral measure of abuse liability, is highly stable and associated with level of dependence, and predicts level of exposure to harmful tobacco-related toxicants²⁵⁻²⁷. To corroborate 12-hour nicotine abstinence prior to visits 2 and 3, e-cigarette urges/craving will be measured using the 10-item Tiffany-Drobes Questionnaire of Smoking Urges: Brief Form ²⁸. A modified version (replacing the word "cigarette" with "e-cigarette") for e-cigarette users and use conditions. Additionally, nicotine withdrawal will be assessed using the empirically validated 15item version of the Minnesota Nicotine Withdrawal Scale²⁹.

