 $[^{11}C]$ -nicotine formulated with a specific eLiq (protonated or free-base) will be produced at the Wake Forest PET Research Center. Subjects will be inhaling a single puff of vapor containing $[^{11}C]$ -nicotine in either protonated or free-base e-Liquid (10 µL). Dynamic 0-15 min PET imaging will be obtained in the head-neck regions followed by a 5 min chest (oral cavity-lungs) scan. The same scan will be repeated with both the e-liquid formulations with 0-15 min chest and 5 min head scans. The subject will be scanned for 15 min in a sequence of 245 frames of 1-4 sec each. Followed by it, a 5 min scan is obtained from regions below the head i.e., oral cavity, trachea, esophagus, bronchi and lungs. All the images will be conducted using GE PET/CT Discovery MI DR scanner. Whole brain radioactivity will be calculated as a percentage of total absorbed dose

per kilogram of brain tissue. Standard uptake values (SUVs), Time activity curves (TACs), and percent variance in total radioactivity will be determined and compared at each time point.

Table 3: Study Measures and Outcomes				
Visit	1	2	3	
Background Measures				
Additional Screening	Х			
Sociodemographic Measures	Х			
Tobacco Use History/Dependence	Х			
NicAlert Test Strip	Х			
Medical History	Х			
Abuse Liability				
EC Topography		Х	Х	
Drug Effects/Liking Questionnaire		Х		
Modified Cigarette Evaluation Questionnaire (mCEQ)		Х		
Tiffany-Drobes Questionnaire of Smoking Urges: Brief Form (modified)		Х	Х	
Minnesota Nicotine Withdrawal Scale		Х	Х	
Biomarkers of Exposure/Effect				
Exhaled Carbon Monoxide	Х	Х	Х	
Procedures				
Pregnancy Test	Х	Х	Х	
PET/CT Imaging		Х	Х	

I. Statistical Methods

i. Power Analysis and Data Analytic Plan

The present study is a pilot study that will be used for preliminary data for a larger R01 submission. Assuming an alpha value of 0.05 and a power of 0.8, a sample size of at least 8 participants is required to observe significant differences in the dose released. As a result, larger populations are likely required in order to evaluate a significant difference between the groups. If the power is set to 0.95 to account for this, then the number of participants required per group is 14. In order to ensure significance and to account for any participants that do not comply, a total of 30 participants is required.

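### The liking questionnaire and the mCEQ are scheduled at Visit 2 only, so the planned within-person comparison of liking and satisfaction would have no session pairs

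*Combined protocol and SAP*

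**What the plan says.** - **Section H, Table 3 (abuse-liability rows).** The "Drug Effects/Liking Questionnaire" and the "Modified Cigarette Evaluation Questionnaire (mCEQ") carry a mark under Visit 2 only. In the same block, topography, smoking urges and withdrawal are marked at Visits 2 and 3, as is PET/CT imaging further down.
- **Section H, text.** The section opens with "All measures, summarized in Table 3", so the table is meant to be the full schedule. It says the liking questionnaire "will assess the desire and liking of both study products". It does not say this of the mCEQ.
- **Section E.ii, Visit #2.** "Participants will also complete a questionnaire assessing several measures of evaluating the perceived abuse liability of the study e-liquids". Neither the timing relative to the puff nor the form to be rated is stated.
- **Section E.ii, Visit #3.** "Visit #3 is essentially identical to Visit #2", and the one difference named is the nicotine form.
- **Section B.** Liking/satisfaction is the self-report part of the abuse-liability outcome, and H1b predicts greater abuse liability with the salt.
- **Section I.i.** Participants act as their own controls. Liking/satisfaction is among the outcomes to be compared. Subjective effects are compared between free-base and salt per laboratory session in a mixed model, which the plan says amounts to a paired t-test or a signed-rank test.

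**The concern.** A paired, session-level comparison needs a rating from the free-base session and one from the salt session. Under Table 3 each participant supplies ratings at only one of the two scanning visits, and that visit uses only one form.

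The schedule is likely to reach the clinic floor. Section G says "each visit will have its own checklist of specific measures to be completed and the order in which they are to be administered". If the Visit 3 checklist is built from Table 3, the second form's liking and mCEQ ratings are not taken, and they cannot be recovered later. The self-report arm of H1b would then lose its planned analysis. The pilot, which is meant to provide preliminary data for a larger application, would also give no within-person variance for these scales.

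**Working it through.** **Setting the passages side by side**

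1. Sections E.i and E.ii: the Visit 2 form is randomised and Visit 3 uses the other form, so there is one form per scanning visit.
2. Table 3: liking and mCEQ at Visit 2 only.
3. From 1 and 2, if each person rates that day's form, every participant has ratings for one form. The number of session-level pairs is 0.
4. Section I.i needs pairs. Section E.ii implies that the questionnaire is repeated at Visit 3. Both conflict with 2.
5. A fault in reading the table is unlikely: the rows directly above and below these two show their Visit 3 marks.

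**What the loss would cost (illustration)**

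There is no figure in the plan to reproduce. The sample size in Section I.i is stated for dose released, with no effect size or SD, and no power is planned for liking.

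Inputs from the documents: up to 30 participants, 20% attrition (Section F.i), two-sided tests, alpha 0.05. Completers: 30 × 0.8 = 24.

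Assumptions: equal split of forms at Visit 2, common SD of 1, and within-person correlation ρ of 0.3, 0.5 or 0.7.

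Standard error of the free-base minus salt difference, in SD units:

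- Between persons, √(2/n per form): 12 vs 12 gives √(2/12) = 0.408. With all 30 rated at Visit 2, 15 vs 15 gives √(2/15) = 0.365.
- Paired, √(2(1 − ρ)/24): √(1.4/24) = 0.242, √(1.0/24) = 0.204 and √(0.6/24) = 0.158 for ρ = 0.3, 0.5 and 0.7.

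| ρ | Paired SE (24) | Ratio, 12 vs 12 | Ratio, 15 vs 15 | Detectable at 80% power, paired |
|---|---|---|---|---|
| 0.3 | 0.242 | 1.7 | 1.5 | 0.71 SD |
| 0.5 | 0.204 | 2.0 | 1.8 | 0.60 SD |
| 0.7 | 0.158 | 2.6 | 2.3 | 0.46 SD |

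Detectable differences come from the noncentral t distribution with noncentrality δ/SE. Between persons they are 1.20 SD (12 vs 12, 22 df) and 1.06 SD (15 vs 15, 28 df).

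Power at δ = 0.597 SD, the paired detectable difference at ρ = 0.5:

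- Paired: 0.597/0.204 = 2.93 on 23 df, power 80%.
- 15 vs 15: 0.597/0.365 = 1.64 on 28 df, power 35%.
- 12 vs 12: 0.597/0.408 = 1.46 on 22 df, power 29%.

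Even at ρ = 0, the 12 vs 12 standard error is √2 = 1.41 times that of 24 pairs.

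**The case against.** The best defence is that both forms are meant to be rated once, at Visit 2. By then participants have sampled the e-liquids at Visit 1 and been given "1 pod of each test e-liquid to take home and practice using at least 3 days". The Visit 2 text refers to e-liquids in the plural, its questionnaire sentence comes before the description of the puff, and Section H says the liking questionnaire covers both products. On that reading Table 3 is coherent and a within-person contrast exists.

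The reading is possible, but it does not remove the conflict. No passage states it as the plan. The plural may be generic, and the both-products wording is not applied to the mCEQ. The contrast would rest at least partly on Visit 1 sampling and home practice, not on the randomised sessions, and it does not fit a per-session analysis. If it is what was meant, Section I.i and the Visit #3 text have to change instead.

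Three further points:

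- Table 3 is incomplete elsewhere (Visit 1 topography is collected but not marked), so the blanks may be clerical and staff may work from the visit text. That is plausible, and the visit checklists are not in the documents, so the data loss is a risk and not a certainty. It is also a reason to correct the table.
- The mixed model tolerates some missing values. It cannot supply within-person pairs when every second rating is absent by design.
- The impact is bounded: the other abuse-liability measures are collected under both forms, and the study is a pilot. This stands and limits the weight of the point.

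**Conclusion.** The inconsistency is real, and at least one passage must change on any reading. The point should be fixed, but it is confined to two instruments.

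The size applies only if Table 3 governs and each person rates that day's form. The liking and satisfaction comparison would then stay unconfounded, because form is randomised at Visit 2, but its standard error would be about 1.5 to 2.6 times that of the planned paired analysis. That range depends on the assumed correlations, the equal split, and whether 24 or 30 people are rated. If the questionnaires are in fact repeated at Visit 3, nothing is lost and only the table is wrong.

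**What to change.** In Table 3, mark the Drug Effects/Liking Questionnaire and the mCEQ at Visit 3 as well as Visit 2. In the Visit #2 and Visit #3 text, add one sentence: both instruments are completed after that visit's puff, following the same one of the two bouts at each visit, and rate that visit's e-liquid. Any pre-puff administration can stay as the baseline for a post-minus-pre analysis. Then check that the Visit 3 checklist carries both instruments.

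The cost is two table marks, one sentence, and a few more minutes on the tablet at a visit participants already attend.

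If the sponsor does intend a single Visit 2 rating of both forms, the protocol should say so for each instrument, and the Section I.i analysis and the Visit #3 description should be rewritten to match. That would give up the comparison tied to the randomised sessions.
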